6.4. Covariates and Subgroups

Subgroup analyses for the main efficacy outcomes (i.e. the primary and key secondary analyses) will evaluate the treatment effect across the following subgroups:

- Geographic region:
 - US sites; Non-US sites
 - North American sites; Asian sites; European sites
- Duration of symptoms prior to enrollment
 - Quartiles
 - ≤ 10 days; > 10 days
 - \leq Median; $>$ Median
- Race (White; Black/African American; Asian; Other)
- Comorbidities
 - None; Any
 - None, One, Two or more
 - Obese; Non-Obese
- Age (<40 ; 40-64; 65 and older),
- Sex (Female; Male),

- Severity of disease
 - Randomization stratification: Mild/Moderate; Severe.
 - Actual disease severity at baseline: Mild/Moderate; Severe
 - Baseline ordinal scale category: 4; 5; 6; 7

Additionally, main analyses of all secondary outcomes will evaluate the treatment effect across the following subgroups:

- Duration of symptoms prior to enrollment (\leq Median; $>$ Median)
- Severity of disease
 - Randomization stratification: Mild/Moderate; Severe.
 - Actual disease severity at baseline: Mild/Moderate; Severe
 - Baseline ordinal scale category: 4; 5; 6; 7

The analyses of time to improvement will also be repeated in the subset of the randomized subjects who enrolled with a baseline clinical score of 7. As part of these analyses, the sensitivity analyses described in Section 3.3.4 regarding unblinded and retreated subjects will be performed in this subset, as well.

There will also be a sensitivity analysis of the primary, key secondary, and mortality outcomes to evaluate the effect of concomitant therapy including experimental treatment and off-label use of marketed medications that are intended as treatment for COVID-19 and are given to patient prior to and during the study. Subjects who report use of the following categories of therapies/treatments will be censored at the time of the earliest start date of any of the therapies/treatments:

- Protease inhibitors
- Polymerase inhibitors
- Other drugs used to treat COVID (off-label, experimental use)
- Corticosteroids
- Other anti-inflammatory drugs:
 - JAK inhibitors
 - Tyrosine kinase inhibitors
 - TNF inhibitors
 - Interleukin inhibitors
 - Interferons
 - Plasma
 - Immunoglobulins
 - T-cell therapies (anti-PD-1 monoclonal antibodies)

- Selective T-cell co-stimulation blockers
- B-cell therapies (CD 20 monoclonal antibodies)

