8.2. Secondary Efficacy Analyses

This section describes the planned analyses for the secondary efficacy outcome measures. Where applicable, refer to Section 6.1 for SAS pseudocode. Analyses of mortality will be described in Section 9.4.

Analyses of the key secondary outcome measure will be explored in the specified subgroups described in Section 6.4. Analyses of the other secondary outcome measures will be performed by treatment arm only and repeated for specified subgroups described in Section 6.4 and Section 6.7 via stratified analyses. As with the analyses described in Section 8.1.2, tabular summaries will follow the structure of the main tabular summaries planned for each outcome with the modification that stratified estimates will be provided in separate rows. Forest plots will display confidence intervals of outcomes/estimates across subgroups, where applicable.

All secondary efficacy analyses will be performed in the ITT population. Treated analyses will be explored to investigate consistency of results compared to the ITT analyses.

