8.2.1. Ordinal Scale Outcomes (Key Secondary Outcome Measure)

For the analysis of the key secondary outcome measure, the distribution of the 8-point ordinal clinical status scale with 8 categories at Study Visit Day 15 (not necessarily actual study day 15), the outcome will be analyzed using a proportional odds model with treatment arm and disease severity as covariates. The treatment odds ratio estimated from the model will be presented along

with the p-value (Table 24). Predicted individual probabilities of scale levels by treatment arm and disease severity will be summarized graphically (Figure 10).

As noted in Section 3.3, sensitivity analyses will be performed to account for subjects who are unblinded as well as placebo subjects who are unblinded and crossover treated with remdesivir. These analyses will be performed in the ITT population.

Multiple supplemental analysis of this key secondary outcome will be performed. Time to improvement by at least one category in the clinical status 8-point scale (see Section 3.3). The log rank test will be performed using a Cox proportional hazards model to test whether the curves differ between treatment arms. The median time to event and CI in each treatment group will be summarized along with the treatment hazard ratio estimate and log rank p-value (Table 26). Differences in time-to-event endpoints by treatment arm will be summarized with Kaplan-Meier curves (Figure 11). Number at risk, hazard ratio and log rank p-values will be presented on the figures. The analyses (and tabular and graphical summaries) will be repeated using the outcome of time to improvement in two categories of the ordinal scale defined in Section 3.3. Both time to improvement (one and two categories) analyses will be repeated using the censoring plan described in Section 3.3 for subjects who are retreated with remdesivir (Table 28). In addition, a subgroup analysis time to improvement among subjects enrolled with a clinical score of 7 will be performed using the retreatment censoring plan (Table 29).

The above analyses will be repeated with the following modification to the ordinal scale described in Section 4.3 (Table 29).

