Treatment Group	Grouping Variable	Subgroup	Recovered		Did Not Recover		Deaths		Not Recovered or Died	
			n	%	n	%	n	%	n	%
Remdesivir (N=X)	Disease Severity	Mild/Moderate	x	x	x	x	x	x	x	x
Placebo (N=X)			x	x	x	x	x	x	x	x
Remdesivir (N=X)		Severe	x	x	x	x	x	x	x	x
Placebo (N=X)			x	x	x	x	x	x	x	x
Remdesivir (N=X)		Any Severity	x	x	x	x	x	x	x	x
Placebo (N=X)			x	x	x	x	x	x	x	x
Continue for duration of symptoms categories in Section 6.4										
N= Number of subjects in the ITT Population.										

Implementation Note: For the symptom categorizations, the Grouping Variable column will display “Duration of Symptoms prior to enrollment”.

Table 23: Odds Ratio for Inferior Clinical Status Score at Study Visit Day 15 by Treatment Using a Proportional Odds Model – ITT Population

Covariate	Treatment Group	Odds Ratio		P-value
		Estimate	95% CI	
Disease Severity	Remdesivir (N=X)	x.x	x.x, x.x	0.xxx
	Placebo (N=X)			
[Continue for each Section 6.4 subgroups]	Remdesivir (N=X)	x.x	x.x, x.x	0.xxx
	Placebo (N=X)			
The specified covariates were included individually in separate models.				

Table with similar format:

Table 24: Odds Ratio for Inferior Clinical Status Score at Study Visit Day 15 by Treatment Using a Proportional Odds Model – Treated Population

Table 25: Odds Ratio for Inferior Clinical Status Score at Study Visit Day 15 by Treatment Using a Proportional Odds Model – Unblinding and Crossover Treatment Sensitivity Analysis – ITT Population

Table 26: Time to Improvement on the 8-Point Ordinal Scale by Treatment Group

Analysis Population	Treatment Group	n	Median Time		HR		P-value
			Estimate	95% CI	Estimate	95% CI	
Improvement by at least One Category							
ITT Population	Remdesivir (N=X)	x	x.x	x.x, x.x	x.x	x.x, x.x	x.xxx
	Placebo (N=X)	x	x.x	x.x, x.x			
Treated Population	Remdesivir (N=X)	x	x.x	x.x, x.x	x.x	x.x, x.x	x.xxx
	Placebo (N=X)	x	x.x	x.x, x.x			
Improvement by at least Two Categories							
ITT Population	Remdesivir (N=X)	x	x.x	x.x, x.x	x.x	x.x, x.x	x.xxx
	Placebo (N=X)	x	x.x	x.x, x.x			
Treated Population	Remdesivir (N=X)	x	x.x	x.x, x.x	x.x	x.x, x.x	x.xxx
	Placebo (N=X)	x	x.x	x.x, x.x			

N = Number of subjects in the specified treatment group and analysis population.
n = Number of subjects with improvement.
HR is the hazard ratio from the Cox Model
P-value calculated using the Log-rank test

Tables with similar format:

Table 27: Time to Improvement on the 8-Point Ordinal Scale by Treatment Group: Remdesivir Retreatment Sensitivity Analysis

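### The Table 23 shell fits the Section 6.4 subgroup variables as covariates, so the planned subgroup analysis of Day 15 status has no output that shows a subgroup effect

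*SAP*

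**What the plan says.** SAP Section 6.4 makes the commitment: "Subgroup analyses for the main efficacy outcomes (i.e. the primary and key secondary analyses) will evaluate the treatment effect across the following subgroups". The list runs from geographic region to severity and ends with "Baseline ordinal scale category: 4; 5; 6; 7". Section 8.2 adds: "Analyses of the key secondary outcome measure will be explored in the specified subgroups described in Section 6.4".

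For the main analysis, Section 8.2.1 states that "the outcome will be analyzed using a proportional odds model with treatment arm and disease severity as covariates". The model statement in Section 6.1 has treatment and one stratification variable as main effects. It has no interaction term and no fit within subgroups.

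The Appendix 1 shell for this endpoint is Table 23, with Tables 24 and 25 in similar format. Its first column is headed Covariate. The worked row, Disease Severity, carries one odds ratio, one confidence interval and one p-value for the comparison of arms. The next row reads "Continue for each Section 6.4 subgroups", and the footnote reads "The specified covariates were included individually in separate models".

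**The concern.** Adjusting for a variable and estimating the effect within its levels are different analyses. A model with treatment plus age group gives one treatment odds ratio, averaged over the age groups. It does not say what the effect is in any age group. A programmer who follows Table 23 would deliver adjusted overall effects where Section 6.4 asks for effects by subgroup.

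At stake is whether the Day 15 effect can be seen to vary with, for example, baseline ordinal category or symptom duration. The rows carry the subgroup variables' names, so they could also be misread as subgroup results.

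**Working it through.** **1. The plan's own figure for this model.** The key secondary sample size uses N = 12(z_α/2 + z_β)² / [λ²(1 − Σp³)]. The inputs are two-sided 5%, 85% power, an odds ratio of 1.75, and Scenario 1 averaged over arms (SAP Section 5).
- 12 × (1.960 + 1.036)² = 107.74
- λ² = (ln 1.75)² = 0.3132
- Σp³ = 0.1268, so 1 − Σp³ = 0.8732
- N ≈ 394, against 396 stated

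The plan's odds ratio is thus a single overall shift. The point below does not depend on this figure.

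**2. Count of what Section 6.4 asks for.**

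| Variable | Groupings | Levels |
|---|---|---|
| Region | 2 | 2 + 3 = 5 |
| Symptom duration | 3 | 4 + 2 + 2 = 8 |
| Race | 1 | 4 |
| Comorbidities | 3 | 2 + 3 + 2 = 7 |
| Age | 1 | 3 |
| Sex | 1 | 2 |
| Severity | 3 | 2 + 2 + 4 = 8 |
| Total | 14 | 37 |

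**3. What the shell gives.** Each row fits logit P(Y ≤ j) = α_j + βT + γX, with T the arm and X one grouping variable. There is one β per model, hence 14 overall odds ratios and 0 of 37 subgroup odds ratios. A subgroup effect needs a separate β in each level, or a T×X term.

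**4. Whether another output fills the gap.**
- Tables 16–17 (time to recovery), 30–33 (time to improvement) and 37–38 (discharge or NEWS) are within-subgroup tables. Day 15 status has none.
- The listed forest plots, Figures 6–8, are all for time to recovery.
- Figure 10 shows predicted probabilities by arm and severity, but the specified model has one common treatment odds ratio, so it cannot show a different effect by severity.

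**5. Illustration.** Trials were simulated with Scenario 1 cut-points, 80% severe, and baseline category, age and comorbidity prognostic. All of these except the Scenario 1 percentages are assumptions. There is one simulated trial per line, and an odds ratio above 1 favours treatment. Each row was fitted as treatment plus that one variable.

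| True odds ratio, mild/moderate and severe | N | Range of 14 rows | Within mild/moderate | Within severe |
|---|---|---|---|---|
| 1.75 and 1.75 | 6,000 | 1.49–1.64 | 1.56 | 1.54 |
| 1.0 and 2.0 | 6,000 | 1.53–1.63 | 0.86 | 1.76 |
| 0.5 and 2.0 | 6,000 | 1.41–1.49 | 0.58 | 1.75 |
| 0.5 and 2.0 | 572 | 1.27–1.44 | 0.65 | 1.64 |

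The row range in the second line lies inside that in the first, so the shell cannot separate a uniform effect from one confined to severe disease. In the third line the effects run in opposite directions and every row still shows a moderate benefit. The within-stratum values differ from the assumed ones partly because other prognostic factors are left out of those fits (odds ratios are non-collapsible).

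**The case against.** The best defence is that the text plans the analysis and only a mock-up is loose. SAP Section 17 allows presentation to change and further tables to be added. Cross-references to shells are visibly imprecise: Section 8.2.1 cites Table 24 for what the list calls Table 23. The row instruction could be read as one row per subgroup. Covariate adjustment is also partly intended, since Section 6.4 covers covariates as well as subgroups.

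Some of this stands: the fault is in the shell, and the subgroup analysis is exploratory. But Section 17 specifies no extra table and says key content stays unchanged. The worked Disease Severity row has a single odds ratio, and the footnote calls the entries covariates. Section 6.4 plans adjustment for continuous age and symptom duration as a separate analysis.

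Three stronger readings are not supported.
- A reader might infer that Section 8.2 promises this endpoint "with the modification that stratified estimates will be provided in separate rows" and forest plots. The first phrase follows a sentence about the other secondary outcomes, and the forest-plot sentence is qualified: "Forest plots will display confidence intervals of outcomes/estimates across subgroups, where applicable". The firm commitment is in Section 6.4.
- A reader might infer that the 14 rows repeat one number. They share a target, but odds ratios are non-collapsible. In the 572-subject illustration the p-values ran from 0.015 to 0.116.
- A reader might infer that 14 p-values inflate the error rate of the key secondary test. Section 8.2.1 designates the severity-adjusted model and no rule uses the smallest p-value. The chance that some row falls below 0.05 depends on assumed prognostic strengths that the documents do not give.

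**Conclusion.** The point holds as a conflict between Section 6.4 and the only output specified for it. Followed as written, Tables 23 and 24 each give 14 differently adjusted overall odds ratios and none of the 37 subgroup odds ratios, and they cannot show heterogeneity. Table 25, the unblinding and crossover sensitivity analysis, inherits the layout only through the similar-format note.

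The counts come directly from Section 6.4 and rest on reading the shell as its footnote and worked row indicate. The simulated odds ratios only illustrate the size of what could be hidden. The primary endpoint's subgroup outputs and the severity-adjusted key secondary result are unaffected. This should be corrected, but it does not threaten the trial's main conclusions.

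**What to change.** - In Tables 23–24, mark the severity-adjusted row as the main key secondary result.
- Add a table of the Day 15 odds ratio within subgroups and a matching forest plot, in the style of Tables 16–17 and Figure 6. For each of the 37 levels, give the treatment odds ratio and 95% confidence interval from a proportional odds model fitted within that level.
- Include severity as a covariate only where it varies within the level. Omit it for the severity levels and for baseline categories where it is constant. Under Protocol Section 6.3 any oxygen or ventilation requirement counts as severe, so categories 5, 6 and 7 should be constant apart from stratification errors.
- Add one treatment-by-subgroup interaction test per grouping. Protocol Section 9.4.7 plans such tests for the primary outcomes only, so this is an addition.
- If covariate-adjusted overall odds ratios are kept, label them as such.

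Cost: a revised shell, one extra table and one extra figure. No new data are needed.

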2.3.4 Assessment of Potential Risks and Benefits

Remdesivir is generally a well-tolerated medication. There are liver toxicities that have been observed in prior studies. These have been self-limited and resolved after cessation of the medication. There is the potential for renal toxicities as observed in pre-clinical data. By excluding those with elevated liver transaminases and decreased kidney function (eGFR < 30 ml/min or requires hemodialysis or hemofiltration), and appropriate monitoring during the study, we can minimize the risk to subjects. While there may not be benefits for an individual subject, there may be benefits to society if a safe, efficacious therapeutic agent can be identified during this global COVID-19 outbreak. The potential risks therefore are thought to be acceptable given the potential benefits.

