9.3. Adverse Events

For the calculation of incidence of adverse events (i.e., on a per subject basis), each subject will only be counted once and any repetitions of adverse events within a subject will be ignored; the denominator will be the number of subjects in the Treated population. All adverse events reported will be included in the summaries and analyses.

An overall summary by treatment arm and disease severity of adverse events is presented that includes subjects with at least one event, at least one related event, at least one SAE, at least one related SAE and at least one AE leading to early termination (Table 57).

Adverse events occurring in 5% of subjects (by MedDRA preferred term) in any treatment group will be presented (Table 58).

The proportion of subjects reporting at least one adverse event will be summarized by MedDRA system organ class and preferred term for each treatment arm, disease severity and overall. Denominators for percentages are the number of subjects in the Treated population.

The following summaries for adverse events will be presented by MedDRA system organ class, preferred term, disease severity and treatment group:

- Subject listing of non-serious adverse events (Listing 11);
- Bar chart of non-serious related adverse events by severity and MedDRA system organ class (Figure 21);
- Bar chart of non-serious related adverse events by maximum severity and MedDRA system organ class (Figure 22);

All the summaries described in this section will be generated for both the early and the full analysis sets.

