9.4. Deaths, Serious Adverse Events and other Significant Adverse Events

A listing of death and other serious adverse events will be presented, including Subject ID, treatment group, Adverse Event Description, Associated Dose Number, Number of Days Post Dose (Duration), Number of Days Post Dose the Event Became Serious, Reason Reported as an SAE, Severity, Relationship to Treatment, Alternate Etiology if not Related, Action Taken with

Study Treatment, Subject Discontinuation, Outcome, MedDRA SOC, and MedDRA PT (Listing 12 and Listing 13).

The number of subjects who die by Day 15 and Day 29 will be presented by treatment arm. The 14- and 28-day crude mortality rate, which will use the number of subjects in the treatment group and analysis population as the denominator, will be presented (Table 59). The analysis will be repeated censoring placebo subjects who were retreated with remdesivir at the time of retreatment.

Mortality through Day 15 and 29 will also be analyzed as a time to event endpoint (see Section 3.3). A table will present median time to event along with 95% confidence intervals overall for each treatment arm along with the hazard ratio estimate and log rank p-values (Table 61). Differences in time-to-event endpoints by treatment will be summarized with Kaplan-Meier curves (Figure 23). Analyses of mortality will be performed in the ITT and the Treated analysis populations and will be performed on both the early and the full analysis sets.

The ITT tabular summaries will be repeated censoring placebo subjects who were retreated with remdesivir at the time of retreatment. Similarly, the summaries will be repeated censoring subjects who were unblinded at the time of unblinding.

Rates of Grade 3 and 4 AE occurrence will be compared between treatment arms using Barnard's exact test and presented (Table 63). Rates of SAE occurrence will also be compared between treatment arms using Barnard's exact test and presented. Further, the composite endpoint of the occurrence of death, SAE, or Grade 3 or 4 AE described in Section 3.3 will be analyzed as a time to event outcome. A table will present median time to event along with 95% confidence intervals overall for each treatment arm along with the hazard ratio estimate and log rank p-values (Table 64). Differences in time-to-event endpoints by treatment will be summarized with Kaplan-Meier curves (Figure 24).

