At least one serious adverse event	X	x	x	x	x	x	x	x	x	x	x	x	x	x	x	x	x	x
At least one related serious adverse event	X	x	x	x	x	x	x	x	x	x	x	x	x	x	x	x	x	x
At least one adverse event leading to early termination ^b	X	x	x	x	x	x	x	x	x	x	x	x	x	x	x	x	x	x
At least one Unanticipated Problem	X	x	x	x	x	x	x	x	x	x	x	x	x	x	x	x	x	x
N = Number of subjects in the Treated Population																		
^a Subjects are counted once for each category regardless of the number of events.																		
^b As reported on the Adverse Event eCRF.																		
All Grade 3 and 4 AEs are captured as AEs. In addition, any Grade 2 or higher suspected drug-related hypersensitivity reaction is reported as an AE.																		

Table 58: Adverse Events Occurring in 5% of Subjects in Any Treatment Group by MedDRA System Organ Class and Preferred Term, and Treatment Group - Treated Population

Preferred Term	MedDRA System Organ Class	Remdesivir (N=X)			Placebo (N=X)			All Subjects (N=X)		
		n	%	Events	n	%	Events	n	%	Events
Serious Adverse Events										
PT1	SOC1	x	x	x	x	x	x	x	x	x
Etc.	Etc.	x	x	x	x	x	x	x	x	x
Other (Non-serious) Adverse Events										
PT1	SOC1	x	x	x	x	x	x	x	x	x
Etc	Etc	x	x	x	x	x	x	x	x	x
N = number of subjects in the Treated Population (number of subjects at risk). n = number of subjects reporting event. Events = total frequency of events reported.										

Programming Notes:

Select all preferred terms/System organ classes where the % for any treatment group or overall is $\geq 5\%$.
Sort preferred terms by descending order of frequency.

Table 59: Deaths by Day 15 or Day 29 by Treatment Group

Analysis Population	Study Day	Remdesivir (N=X)			Placebo (N=X)		
		n	Mortality Rate	Rate 95% CI	n	Mortality Rate	Rate 95% CI
ITT Population	Day 15	x	x.x	x.x, x.x	x	x.x	x.x, x.x
	Day 29	x	x.x	x.x, x.x	x	x.x	x.x, x.x
Treated Population	Day 15	x	x.x	x.x, x.x	x	x.x	x.x, x.x
	Day 29	x	x.x	x.x, x.x	x	x.x	x.x, x.x

N = Number of Subject in the specified treatment group and analysis population.
n = Number of subjects in a given treatment group who died by the given timepoint

Table with similar format:

Table 60: Deaths by Day 15 or Day 29 by Treatment Group – Unblinding and Crossover Treatment Sensitivity Analysis

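### The 5% cut in SAP Table 58 also covers serious adverse events, and no other numbered table shell gives adverse-event preferred terms by arm

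*SAP*

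**What the plan says.** The Table 58 shell (SAP Appendix 1) is titled "Adverse Events Occurring in 5% of Subjects in Any Treatment Group by MedDRA System Organ Class and Preferred Term, and Treatment Group". It has one block for serious adverse events and one for other, non-serious events, each with subjects, percentage and events by arm. A single programming note governs both: "Select all preferred terms/System organ classes where the % for any treatment group or overall is" at least 5%.

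SAP Section 9.3 introduces the table in the same terms: "Adverse events occurring in 5% of subjects (by MedDRA preferred term) in any treatment group will be presented". Neither place sets a different rule for serious events.

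Section 9.3 also contains two statements with no threshold. One is general: "All adverse events reported will be included in the summaries and analyses". The other says that the proportion of subjects with at least one adverse event "will be summarized by MedDRA system organ class and preferred term for each treatment arm, disease severity and overall". That second sentence cites no table, and the Appendix 1 list has no shell for it. The items that follow it in Section 9.3 are a listing of non-serious events and two bar charts of non-serious related events (Figures 21 and 22).

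Section 9.4 covers serious events individually: "A listing of death and other serious adverse events will be presented, including Subject ID, treatment group, Adverse Event Description", together with the preferred term (Listings 12 and 13).

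**The concern.** A frequency cut keeps a table of common, mostly non-serious events readable. Applied to serious events it removes the rows where a by-arm comparison of individual terms is most useful. A serious term can differ clearly between arms and still stay below 5% in both.

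The cumulative incidence of serious adverse events is a named secondary safety objective in both documents. If the shells are programmed as written, the report shows how many subjects in each arm had any serious event. It does not show which serious terms account for a difference, unless a term reaches 5%. In a severely ill population, the count of subjects with any serious event can mask an imbalance in one term.

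**Working it through.** **Which outputs give serious preferred terms by arm**

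| Output | Content | Serious preferred terms by arm? |
|---|---|---|
| Table 57 | Subjects with at least one event of each type | No |
| Table 58 | Preferred terms by arm, serious and non-serious blocks | Only at 5% or more |
| Table 63 | Any Grade 3 or 4 event; any serious event | No |
| Table 64 | Time to a composite safety endpoint | No |
| Tables 65 and 66 | Laboratory parameters | No clinical terms |
| Figures 21 and 22 | Non-serious related events by system organ class | No |
| Listings 12 and 13 | Each serious event or death, with arm and preferred term | No count or rate |
| Section 9.3 sentence, no shell | System organ class and preferred term by arm, no cut | Terms yes, but serious not separated |

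**Inputs for the size of the gap**

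- Cut: 5% in either arm or overall (Table 58 note).
- Denominator: the Treated population (SAP 9.3).
- Allocation: 1:1 (SAP 4.2.3).
- Total sample size: 600 to over 800 (SAP 4.1), so about 300 to over 400 per arm. The documents give no treated number per arm, so N below is an assumption. 286 is half of the protocol's projected 572.

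**Largest count that is left out**

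With x events in one arm and none in the other, the overall percentage x/(2N) is half the arm percentage, so the arm percentage decides. The largest omitted count is the largest x with x/N < 0.05. The two-sided Fisher p-value for x versus 0 with equal arms is 2 × C(N, x) / C(2N, x).

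| N per arm | Largest omitted x | Percentage | Fisher p, x versus 0 |
|---|---|---|---|
| 286 | 14 | 4.90% | 1.0e-4 |
| 300 | 14 | 4.67% | 1.0e-4 |
| 400 | 19 | 4.75% | 3.1e-6 |
| 420 | 20 | 4.76% | 1.5e-6 |
| 450 | 22 | 4.89% | 3.7e-7 |

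At 400 per arm, 20/400 = 5.0% would be shown and 19/400 would not. The overall percentage for 19 versus 0 is 19/800 = 2.4%.

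**Less extreme splits at 400 per arm**

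- 19 versus 6 is also omitted (p = 0.013).
- 6 versus 0 already gives p = 0.031, so any split from 6 to 19 versus 0 has a nominal p below 0.05 and no row in the table.

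**Rounding**

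SAP Section 13 reports percentages to the nearest whole number. If the cut is applied after rounding, x/N must be below 4.5%. At 400 per arm, 18/400 = 4.5% rounds to 5% and is shown, so the limit is 17 versus 0 (4.25%, p = 1.3e-5). At 300 per arm it is 13 (4.33%).

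**The case against.** The strongest reply is that the SAP text already plans what is said to be missing. Section 9.3 commits to a preferred-term summary by arm with no threshold, and Section 17 allows additional tables. This stands in part. A reader who looked only at Table 58 might infer that the SAP plans no uncut preferred-term summary by arm, and the documents do not support that. But the sentence has no table number or shell, and it does not say that serious events will be shown separately. Permission to add tables does not commit anyone to produce this one.

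Second, Protocol Section 9.4.4 accepts either a table or a listing for serious treatment-emergent events, and Listings 12 and 13 show every one with its arm and preferred term. This also stands: no serious event disappears from the report, and a reader could count them by hand. What is missing is the count and rate by arm.

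Third, the protocol says "There is the potential for renal toxicities as observed in pre-clinical data" and describes liver findings, so a reader might infer that an imbalance in renal or hepatic toxicity would go untabulated. That goes too far. Table 65 gives Grade 3 and 4 laboratory results by arm, parameter and time point with no frequency cut, and SAP Section 9.6 includes creatinine, eGFR, bilirubin, ALT, AST and PT/INR. Clinical serious terms remain, including hypersensitivity, which has no laboratory marker in those tables.

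Fourth, 19 versus 0 is the most extreme split under the cut, and the p-values are not adjusted for the number of terms examined. Both are true. The p-values show how large an imbalance the table can omit; they do not predict one. The note also names preferred terms and system organ classes together, so a term under 5% might be kept when its class reaches 5%. That is a further ambiguity, and it gives no assurance that serious terms are shown.

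**Conclusion.** The point holds as a gap between the SAP text and its shells. The only numbered table shell with adverse-event preferred terms by arm applies the 5% cut to serious events, and the uncut summary promised in Section 9.3 has no shell and does not separate serious events.

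The limits calculated above rest on the assumed number treated per arm and on a cut applied to unrounded percentages. Rounding lowers them slightly and does not change the conclusion. The documents give no expected frequency for any serious term, so nothing here says how likely such an imbalance is.

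No primary or secondary efficacy inference is affected. This is an inexpensive improvement to the safety report.

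**What to change.** In the Table 58 programming note, restrict the 5% selection to the non-serious block. State that the serious block lists every serious preferred term by arm with number of subjects, percentage and number of events. Amend the table title and the Table 58 sentence in SAP Section 9.3 to match. Additional renal or hepatic rows are not needed, because Table 65 covers the laboratory side.

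The change costs one programming note, two matching text edits and a longer table. It needs no new data.
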